4.3.2 IMP Administration Review and Dose Escalation Criteria and Process

Up to 18 adult participants (as defined in section 5.3) will be administered one of 3 doses of ATIMP in a total maximal volume of 1mL, according to the dose-escalation criteria:

- 1) low dose
- 2) intermediate dose
- 3) high dose

Once a maximal tolerated dose is established, up to 53 further participants aged 5 years or older will continue to be administered ATIMP up to the highest dose observed to be tolerated in adults. This includes up to 5 paediatric participants in the confirmation phase and up to 48 in the randomised phase.

4.3.2.1 Dose Escalation Criteria and Dose Limiting Events

Dose escalation will be undertaken in adults, based on an escalation rule around dose-limiting events (DLEs). An IDMC will review data from a minimum of 9 weeks of follow up from each cohort of 3 participants, before recommending the next dose to be assessed in a further cohort of patients.

A DLE is defined as any of the below occurring during the 9 weeks following administration, at least possibly related to the ATIMP, not surgery alone:

- Reduction in visual acuity by 15 ETDRS letters or more
- Severe unresponsive inflammation (defined below)
- Infective endophthalmitis
- Ocular malignancy
- Grade III or above non-ocular SUSAR (see section 5.11.3)

Severe unresponsive inflammation will be defined according to the Standardisation of Uveitis Nomenclature (SUN) Working Group grading system (Jabs *et Al.* 2005) i.e.

- anterior chamber cells 3+ (26-50 cells in a field size of 1mm x 1-mm slit-beam), or
- anterior chamber flare 3+ (marked, iris and lens details hazy), or
- vitreous haze 3+ (Ophthalmology 1985; 92:467-71)

that fails to improve by 2 steps (or to grade 0) during a 6 week period.

Review of safety data will be undertaken by the IDMC prior to each dose escalation. Children will be included at up to the highest safe anticipated therapeutic ATIMP dose recommended by the IDMC, once a safety profile has been established in adult participants.

4.3.2.2 Dosing Process

4.3.2.2.1 Cohort 1 [administration and immediate follow up is now complete in this cohort]

ATIMP will first be administered at the lowest dose to 1 adult participant only. This participant will be monitored for signs of toxicity for a period of 9 weeks. If there is no DLE as defined above after a minimum of 9 weeks, ATIMP will continue to be administered at the same dose to 2 further adult participants. In the event of a DLE in the 1st adult in the cohort, the cohort will be expanded to a possible total of 6 participants. A discussion will be held with the IDMC to agree a plan of action for administering the ATIMP to further adults. The IDMC will review the data collected on this cohort up to 9 weeks following ATIMP administration to the 3rd participant.

4.3.2.2.2 Cohort 2 [administration and immediate follow up is now complete in this cohort]

In the event that there is no DLE in any participant, the IDMC will recommend administering ATIMP at the intermediate dose level to a single adult participant. If there is no DLE after a minimum of 4 weeks, ATIMP will continue to be administered at the same dose to 2 further adult participants. In the event of a DLE in the 1st adult in the cohort, an additional 3 participants will may be treated at this dose level. A discussion will be held with the IDMC to agree a plan of action for administering the ATIMP to further adults. The IDMC will again review the data available on this next cohort of adult participants up to 9 weeks following ATIMP administration to the 3rd participant.

4.3.2.2.3 Cohort 3 [administration and immediate follow up is now complete in this cohort]

If the IDMC recommends it is safe to dose escalate to the highest dose, then ATIMP will be administered at the highest dose level to a single adult participant. If there is no DLE after a minimum of 4 weeks, ATIMP will be administered at the same dose to 2 further adult participants. In the event of a DLE in one of the 3 participants at this dose, the cohort may be expanded to up to 3 additional participants at this dose level. A discussion will be held with the IDMC to agree a plan of action for administering the ATIMP to further adults.

4.3.2.2.4 Additional considerations

In the event of a DLE in 1 of the 3 participants at a given dose, the cohort may be expanded and additional participants treated at the dose level. The IDMC will review the safety data and confirm that additional participants may be treated at this dose. The dose escalation will continue until:

- On review of the accumulating data the IDMC recommend a maximum dose to be administered in the expansion phase;
- 3 participants have been administered the highest dose without any DLEs; or
- until at least 2 participants among a cohort of 3 to 6 participants experience DLEs (i.e., ≥33% of
 patients with a DLE at that dose level), in which case the recommended maximum anticipated
 therapeutic dose will be the level below.

In the event that 1 or 2 DLEs are seen at the 1st dose level, the IDMC may recommend administering a lower dose to that described in the protocol to a cohort of participants.

[figure not shown]

Table 1: Dose escalation and confirmation table

Number of DLEs	 		
Low dose			
Participants 1-3	Participants 4-6	Action	Details
Intermediate do			
Participants 1-3	Participants 4-6	Action	Details
High dose			
Participants 1-3	Participants >3	Action	Details

Figure 1: Dose escalation Flow chart

4.3.2.2.5 Confirmatory Safety Phase

The adult dose escalation component of the study is complete at the time of protocol amendment v9.0. Review of the data collected to date with the IDMC led to a decision not to pursue the higher dose level and to commence administration for confirmation in paediatrics at the intermediate dose level. Children are defined as those aged 15 and under in the UK, and 17 and under in the US. These participants in the paediatric confirmation phase are administered the intermediate dose

been shown to be well tolerated in adults. Having identified children who may be willing to participate in the study, the CI will prioritise ATIMP administration to older candidates in the 1st instance. The 1st child administered ATIMP will be monitored for safety for a period of 4 weeks. If there is no adverse event consistent with the above definition of a DLE after 4 weeks, ATIMP will be administered to further children.

In order to fully explore dose levels and make optimal use of the expansion phase of the study, a treatment group randomisation will subsequently occur to either low or intermediate dose; to achieve up to 32 participants receiving intervention at baseline, and up to 16 further participants receiving deferred intervention at 6 months following baseline (control group). The expansion phase will include up to 48 participants in total, who may be adults or children.

Therefore, participants will be randomised to 1 of 3 arms in a 1:1:1 ratio (immediate low dose administration (n= up to 16): immediate intermediate dose administration (n= up to 16): deferred administration (n= up to 16)). Participants randomised to the deferred administration group will be further randomised to receive the low or intermediate dose in a 1:1 ratio (deferred low dose administration (n= up to 8): deferred intermediate dose administration (n= up to 8)). The eye selected for administration will also be randomised. All aspects of randomisation will occur on completion of screening. (Figure 2: Randomisation Timeline). Baseline assessments will be completed as soon as possible after randomisation and will be valid for 3 months². In the deferred treatment group, a day 0 will be applied at the end of baseline assessments and deferred treatment follow up will be calculated from this date. The three treatment groups of the randomised expansion phase will be stratified by age at date of informed consent (<25 years, ≥25 years) to balance for disease severity between treatment groups with age used as a surrogate for severity.

_

² For patients who surgery dates were postponed due to COVID 19 please refer to appendix 1

Figure 2: Randomisation Timeline

Time (months)			
0	Participant completes screening Randomisation 1: Eye selected for administration Randomisation 2: Treatment Group		
6 months after completion of baseline assessments in deferred treatment group	Control group administered low or intermediate dose Interim analysis performed 3 and 6 months post- surgery of the last participant in the low or intermediate treatment arm		
12	Follow-up complete		

5 Methods

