4.3 Trial Design

This is an open-label phase I/II dose-escalation trial to determine the safety and efficacy of subretinal administration of AAV2/5-hRKp.RPGR in participants with XLRP caused by mutations in *RPGR*.

In the dose escalation phase, up to 18 adult participants will be administered one of 3 different doses of the ATIMP in cohorts of 3 participants at a time. Based on toxicity data, the IDMC will make a recommendation on the dose to administer to the next cohort of 3 participants.

Adults are defined as participants aged 16+ in the UK and aged 18+ in the US.

Once an acceptable safety profile has been established in adults, the IDMC will agree the maximum tolerated dose in adults before recommending administering up to this dose in the study. This maximum acceptable dose will be confirmed in paediatrics in the first instance.

Subsequent participants in the expansion phase will be randomised to one of 3 treatment groups (low dose administration: intermediate dose administration: deferred administration). Participants randomised to the deferred administration arm will also be randomised to receive either the low or intermediate dose. The eye selected for administration will also be randomised. All aspects of randomisation will be performed on completion of screening. Baseline assessments will be completed as soon as possible after randomisation and will be valid for 3 months¹. See Section 5.9.1 for further details regarding randomisation. The deferred administration treatment group will perform baseline assessments as soon as possible after randomisation. At the end of baseline assessments, a day 0 will be applied and deferred administration follow up will be counted from this date. The deferred treatment group will be considered as a control group.

_

¹ For patients who surgery dates were postponed due to COVID 19 please refer to appendix 1

Safety and efficacy will be assessed for 12 months following the intervention by clinical examination and special investigations according to the schedule in section 5.6.

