5.3.1.6.4 Enrolment (Randomisation)

Participants who fulfil the study entry criteria based on the results of all screening assessments will be enrolled (randomised) in the trial. ATIMP will be administered within 3 months of enrolment for participants randomised to immediate treatment. If the ATIMP is not delivered within 3 months of enrolment, all screening tests with the exception of genetic testing, visual mobility and electrophysiological assessment will be repeated and eligibility for enrolment re-assessed³. For participants randomised to the control (deferred treatment) arm, study assessments will be performed per the Table 4: Trial Assessments (Deferred treatment arm).

Participants who withdraw or are withdrawn from the study for any reason prior to ATIMP administration may be substituted in the study.

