5.9 Assignment of Intervention

5.9.1 Allocation

All participants will receive the same intervention in this open label, non-randomised trial: subretinal administration of AAV2/5-hRKp.RPGR to 1 eye. The dose received by each participant will depend on the order of their enrolment in the trial according to the sequence of dose escalation, and the extent of dose-limiting events. Children will not be enrolled in the trial until the safety profile and recommended dose have been established in adults.

In the randomised expansion phase, a target of up to 48 eligible participants will be randomised in a 1:1:1 ratio to receive immediate low dose administration (n=up to 16), immediate intermediate dose administration (n=up to 16) or deferred administration (n=up to 16). Within the deferred administration treatment group, participants will be further randomised in a 1:1 ratio to deferred low dose administration (n=up to 8) or deferred intermediate dose administration (n=up to 8). The randomisation of treatment will be stratified by age at informed consent (<25 years, ≥25 years), the rationale for the stratification levels is described in Section 4.3.2.2.5 of this document. Thus, the overall randomisation ratio will be 2:2:1:1 (immediate low dose: immediate intermediate dose: deferred low dose: deferred intermediate dose).

The eye of treatment will also be randomised in a 1:1 ratio; this aspect of the randomisation is considered administrative so will not be stratified or balanced across treatment groups, the rationale for this is described in Section 5.4.2.2.2 of this document.

The randomisations will be produced by an independent statistician. The treatment and eye will be allocated in the web-based EDC system.

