1.4. Randomization and Blinding

In dose escalation phase, up to 18 adult participants will be administered one of 3 different doses of the ATIMP in cohorts of 3 participants at a time. Based on toxicity data, the IDMC will make a recommendation on the dose to administer to the next cohort of 3 participants.

Once an acceptable safety profile has been established in adults, the IDMC will agree the maximum tolerated dose in adults, which will be confirmed in 3 pediatric participants.

In the expansion phase, up to 48 subjects were randomized to 1 of 3 arms in a 1:1:1 ratio (Immediate low dose administration: Immediate intermediate dose administration: deferred administration). Subjects randomized to the deferred administration group were further randomized to receive the low or intermediate dose in a 1:1 ratio. The eye selected for administration was also randomized at the start of the expansion cohort. All aspects of randomization occurred on completion of screening. The three treatment groups of the randomized expansion phase will be stratified by age at date of informed consent (<25 years, \geq 25 years) to balance for disease severity between treatment groups with age used as a surrogate for severity.

Visual function assessors and reading centers are masked to treatment (dose levels and immediate vs. deferred treatment). Neither study site nor sponsor personnel were masked to treatment.

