5.3.3. Analysis Methods

Descriptive summaries by treatment group and time point (and study eye when appropriate) using descriptive statistics will be provided. Descriptive statistics such as mean, median, standard deviation, 95% CIs (when applicable), minimum, and maximum will be used to summarize continuous variables; counts and percentages will be used to summarize categorical variables. Change from baseline will be summarized in the same format and plotted across time by treatment group for primary and secondary endpoints.

The primary efficacy endpoint will be evaluated based on point-by-point data from 185-point static perimetry (excluding 3 loci near blind spot). Subjects will be considered a responder if they experience at least 7dB improvement from baseline in at 5 or more loci at Week 13 and Week 26. Subjects with missing visits in either Week 13 or Week 26 will not be counted as responder or non-responder and will not contribute to number of subjects in the denominator when calculating proportion of responders.

A Stratified Fisher's exact test (two-sided) will be used to evaluate the number of responders and non-responders in immediate (pooled low and intermediate doses) versus deferred treatment group

from the dose expansion phase of the study. The stratification factor is age at time of informed consent (<25 years, \geq 25 years). Point estimates with corresponding 95% confidence intervals will be provided for the difference in proportion of responders comparing between immediate vs. deferred treatment group. The proportion of responders and 95% confidence interval at week 52 in immediate treatment group (pooled low and intermediate doses) will also be estimated, where the responder is defined as a subject who experiences at least 7 dB improvement from baseline at 5 or more loci at Week 52 and one or more time point prior to Week 52.

The proportion of responders and 95% confidence interval through week 26 will be estimated and summarized by dose level (low and intermediate) and overall in a separate table for deferred subjects post treatment.

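### The deferred arm's dose is randomised on completion of screening, about 6 to 10 months before it is used, and nothing in the plan withholds it from unmasked staff or participants until Month 6

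*Protocol*

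**What the plan says.** Protocol 4.3 (Trial Design) states: "Participants randomised to the deferred administration arm will also be randomised to receive either the low or intermediate dose". It sets the timing in the same paragraph: "All aspects of randomisation will be performed on completion of screening". Protocol 4.3.2.2.5 repeats the rule: "All aspects of randomisation will occur on completion of screening". Protocol 5.9.1 gives an overall 2:2:1:1 ratio in up to 48 participants. An independent statistician produces the lists, and allocation is made in the web-based EDC system.

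Table 4 (Protocol 5.6) places deferred administration after the Month 6 assessments. A table footnote counts Month 6 from the last baseline visit, which itself follows randomisation. By column position, the eligibility row of Table 4 is marked at screening and again at Month 6. The text gives no criteria for the second check.

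On pre-dose withdrawals, Protocol 5.3.1.6.4 says: "Participants who withdraw or are withdrawn from the study for any reason prior to ATIMP administration may be substituted in the study".

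SAP 1.4 says: "Neither study site nor sponsor personnel were masked to treatment". The sentence just before it says that visual function assessors and reading centres are masked to dose and to immediate versus deferred treatment.

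The deferred dose enters the analysis in SAP 5.3.3, where post-treatment responder proportions are "summarized by dose level (low and intermediate) and overall in a separate table for deferred subjects post treatment". SAP 5.4.2 does the same for V30 and the other secondary endpoints.

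**The concern.** The low-or-intermediate assignment within the deferred arm has no use until product is prepared after Month 6. Protocol 5.4.4 has it diluted to the intended dose immediately before administration. Assigning the dose at the end of screening opens a long interval in which it can be known to people who influence who stays, who is substituted and who is judged eligible at Month 6.

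Information about the doses could also appear during that interval. Protocol 5.11.2 allows an interim analysis at 3 and 6 months, Protocol 6.13.1 allows findings to be presented during the trial, and SAP 3 reports an administrative interim summary of efficacy and safety.

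At stake are the make-up of the two deferred dose groups in the post-treatment tables and, to a lesser degree, who is still evaluable in the control arm at Week 26.

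**Working it through.** **1. Allocation reproduced.** 48 × (2, 2, 1, 1)/6 = 16, 16, 8, 8, which matches Protocol 5.9.1. The deferred arm has 8 + 8 = 16.

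**2. Time from dose assignment to dosing.** This is the baseline period after randomisation plus 6 months to Month 6.
- Baseline takes no time: 0 + 6 = 6 months.
- Three-month baseline (Protocol 4.3.2.2.5): 3 + 6 = 9 months.
- Four-month baseline (Table 4 footnote): 4 + 6 = 10 months.

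If the Month 6 window is taken as ±14 days, the shortest case is about 5.5 months. COVID-19 lengthened the deferral for some (SAP 1.2), and the SAP 2.1 window for the deferred Week 26 visit runs to Day 365, about 12 months from the end of baseline.

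**3. Disclosure.** Set side by side, the randomisation rule, allocation through the EDC system and unmasked site and sponsor staff allow early knowledge of the dose. No text gives a disclosure time, and none withholds the dose.

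**4. Reach into the primary comparison.** It pools the low and intermediate doses and uses deferred participants before treatment (SAP 1.3.2, 2.2, 5.3.3). The Month 6 visit supplies the Week 26 data, and a deferred participant enters the Full Analysis Set with a baseline and one post-baseline visit before administration (SAP 2.3.2). Someone not dosed after Month 6 therefore still counts as a control. Loss before Week 26 is different: SAP 5.3.1 removes anyone missing Week 13 or Week 26 from the denominator.

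**5. Size of a loss (no substitution assumed).**
- One participant: 1/8 = 12.5% of a deferred dose group; 1/16 = 6.25% of the control arm.
- Two from the same dose group: 2/8 = 25%; 2/16 = 12.5%.

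**6. By-dose tables, illustration.** With an assumed 4/8 responders (50%), the exact 95% interval is 16% to 84%. Losing two non-responders gives 4/6 = 67%, a shift of 17 percentage points.

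**7. Primary test, illustration.** The plan states no power, effect size or dropout rate. The figures below use assumed responder rates and an unstratified two-sided Fisher test at 0.05; the SAP's test is stratified by age. Immediate n = 32, with 16, 14 or 12 evaluable deferred participants.
- 40% versus 5%: power 77%, 69%, 65%.
- 50% versus 10%: power 77%, 75%, 70%.

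These show what losing 2 or 4 controls would cost for any reason. They do not suggest that dose-driven loss of that size is likely.

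**The case against.** The strongest reply is that this is a declared open-label trial and that randomising once, at 2:2:1:1, is a coherent design. Several parts of that reply stand.

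- A reader might infer that the dose is released at screening. The documents do not say so. Protocol 5.9.1 says where allocation is made, not when the deferred dose becomes visible. Decisions can be made knowing the dose; it is not shown that they are.
- A reader might call this a failure of allocation concealment. It is not. Screening is complete before randomisation, the list comes from an independent statistician and the EDC system allocates. The issue is early knowledge of a later assignment.
- A reader might infer that visual function testing is compromised. Assessors and reading centres are masked. Deferred participants know that they are untreated until Month 6 in any case, and nothing in the documents shows that knowing low versus intermediate would alter their effort further.
- The by-dose deferred tables lie outside the testing hierarchy in SAP 5.5, and Protocol 5.6.2 describes a highly motivated population. No dose-driven withdrawal is documented.
- The Month 6 eligibility check rests on one table mark with no supporting text, and the column should be confirmed.
- The SAP is based on protocol v12.0, while the amendment log in the protocol reviewed ends at v11.0. Later wording on deferred timing could not be checked.

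What the reply does not supply is a reason for fixing the dose this early, or any rule that withholds it.

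**Conclusion.** The point holds as a minor one, and the remedy is a cheap improvement. The deferred dose is randomised nominally 6 to 10 months before use, with no stated rule to conceal it from unmasked staff or from participants. Retention, substitution and the Month 6 eligibility check can therefore be influenced by it.

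The main exposure is the untested post-treatment estimates, with at most 8 participants per dose. The primary comparison is exposed only through dose-driven loss before Week 26, at 6.25% of the control arm per participant. It would be wrong to conclude that the Month 6 dosing decision biases the primary result: that comparison is pooled, uses pre-treatment data, and already has its Week 26 value by then.

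The conclusion assumes that no other trial document restricts when the dose is disclosed, that the Month 6 mark in Table 4 is read correctly, and, for the percentages, full enrolment of 16 deferred participants without substitution.

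**What to change.** In Protocol 4.3.2.2.5 and 5.9.1, with the matching sentence in 4.3, keep arm and eye randomisation on completion of screening. State that the EDC system releases a deferred participant's dose, from the independent statistician's existing list, only after the Month 6 assessments are complete and eligibility is confirmed. The planned 16/16/8/8, the alpha and the visit schedule do not change. The interval between knowing the dose and giving it falls from about 6 to 10 months to the 14-day administration window in Table 4.

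The cost is one sentence per section and one EDC release setting. Because the product is diluted at the time of surgery, no need for earlier knowledge is apparent, though the ATIMP management plan should be checked. The downside is that participants and sites learn the dose later.

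SAP 1.2 and 1.4 describe expansion randomisation in the past tense. If it is complete, report instead when deferred doses were disclosed, and tabulate pre-dose withdrawals, Month 6 exclusions and substitutions by assigned deferred dose. That costs one table.
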